3.2 Exclusion Criteria

1. Patients with mutations in or deficient expression of one or more of the mismatch repair genes listed: MSH2, MSH3, MSH6, MLH1, PMS1, PMS2.
2. Active infection requiring systemic therapy.
3. Pregnant or breastfeeding (**NOTE:** breast milk cannot be stored for future use while the mother is being treated on study).
4. Second primary malignancy within the last 2 years. Clear exceptions are 1) patient had a second primary malignancy but has been treated and disease free for at least 2 years or is considered likely to be cured by their oncologist if the period has been less than 2 years, 2) *in situ* carcinoma (e.g. *in situ* carcinoma of the cervix, basal or squamous cell skin cancer, and superficial bladder cancer). Patients with chronic lymphocytic leukemia will be allowed if their blood counts are within acceptable hematologic parameters and if they are not currently requiring cytotoxic or biologic anticancer treatment (supportive treatment such as IVIG is permitted).
5. Metastatic disease not limited to the liver.
6. Disease not amenable to complete resection, not resectable within the confines of a single surgery, or where resection would result in inadequate functional liver remnant.
7. Has a known history of immunodeficiency including but not limited to patients with HIV/AIDS and chronic Hepatitis B/C. Testing is not required.
8. Patient with clinically significant cardiomyopathy, coronary disease, heart failure New York Heart Association (NYHA) class III or IV, or cerebrovascular accident (CVA) within 1 year of study enrollment (CV301).

9. Subjects with known severe allergy to eggs, egg products, or aminoglycoside antibiotics (for example, gentamicin or tobramycin) (CV301).
10. Participants with an active, known or suspected autoimmune disease. Participants with type I diabetes mellitus, hypothyroidism only requiring hormone replacement, skin disorders (such as vitiligo, psoriasis, or alopecia) not requiring systemic treatment, or conditions not expected to recur in the absence of an external trigger are permitted to enroll.
11. Participants with a condition requiring systemic treatment with either corticosteroids (> 10 mg daily prednisone equivalent) or other immunosuppressive medications within 14 days of start of study treatment. Inhaled or topical steroids, and adrenal replacement steroid doses > 10 mg daily prednisone equivalent, are permitted in the absence of active autoimmune disease.
12. Participants with history of life-threatening toxicity related to prior immune therapy (e.g. anti-CTLA-4 or anti-PD-1/PD-L1 treatment or any other antibody or drug specifically targeting T-cell co-stimulation or immune checkpoint pathways) except those that are unlikely to re-occur with standard countermeasures (e.g. Hormone replacement after adrenal crisis)
13. Patients with serious or uncontrolled medical disorders.
14. Treatment with botanical preparations (e.g. herbal supplements or traditional Chinese medicines) intended for general health support or to treat the disease under study within 2 weeks prior to randomization/treatment.
15. History of allergy or hypersensitivity to study drug components.
16. Has received a live vaccine within 30 days of the planned start of study therapy. **NOTE:** seasonal flu vaccines for injection are generally inactivated vaccines and are allowed, however intranasal influenza vaccines are live attenuated vaccines and are not allowed.
17. History of allogenic stem cell or solid organ transplant.

4. SUBJECT REGISTRATION

This protocol is open to both men and women and all races. All subjects must be registered through HCRN's electronic data capture (EDC) system. A subject is considered registered when an "On Study" date is entered into the EDC system. Subjects must be registered and randomized prior to starting protocol therapy. Subjects must begin therapy **within 5 business days** of randomization.

4.1 Randomization

1:1 randomization with no stratification.

5. TREATMENT PLAN

The experimental aspect of this protocol is in the use of perioperative CV301 in combination with Nivolumab plus mFOLFOX6 in patients with hepatic-limited metastatic colorectal cancer. mFOLFOX6 is an FDA-approved regimen for perioperative use in patients undergoing surgery for hepatic-limited metastatic colorectal cancer. Nivolumab is a human programmed death receptor-1 (PD-1) blocking antibody approved by the FDA for the treatment of several cancer types. The safety and optimal dosing of PANVAC were established in several tumor types¹³⁻¹⁷. The safety and optimal dosing of CV301 (formally known as PANVAC) has been established in a recent phase I/II clinical trial.

5.1 Sequence of Treatment

5.1.1 Prior to neoadjuvant therapy

Eligible patients must have biopsy-proven isolated liver metastases by radiographic imaging of the investigators' choosing and deemed resectable after multi-disciplinary discussion. After providing informed consent patients will undergo a core biopsy of tumor tissue from the metastatic site for correlative studies. If the patient has already had a prior fine needle biopsy, they will need to undergo a repeat biopsy (core biopsy) to obtain the necessary tissue for correlative studies. We will also collect peripheral blood for both, baseline lab work as well as for the planned correlates. Tissue samples will be reviewed for confirmation of diagnosis and used for molecular studies as described.

5.1.2 Neoadjuvant Therapy

Patients who are eligible for and consent to enroll onto this trial will be randomized to either the control arm or the experimental arm. One cycle is 2 weeks.

- Patients in the control arm (Arm A) will receive mFOLFOX6 and Nivolumab given on Day 1 of every 2 week cycle for 4 cycles (Cycle 1 - Cycle 4). The treatment order for Arm A is Nivolumab followed by mFOLFOX6.
- The experimental arm (Arm B) will receive two doses of Nivolumab and MVA-CV301 each given Days -28, -14, followed by four cycles of Nivolumab plus FPV-CV301 given on Day 1 of every 2 week cycle concurrently with mFOLFOX6, which will again be administered every 2 weeks for 4 cycles (Cycle 1 – Cycle 4). For Arm B the order of administration is Nivolumab followed by the vaccination at least one hour prior to mFOLFOX6.

A window of +2 days between administration of Nivolumab +/- vaccination and mFOLFOX6 is allowed. This window will accommodate subjects that receive their chemotherapy locally. If there is more than a 2-day delay for any reason, administration of study drugs should be re-aligned so that the chemotherapy falls within +2 days with the next cycle.

5.1.3 Surgical Resection

About 2 weeks after neoadjuvant therapy, patients will be re-evaluated for surgical resection with re-staging imaging of the C/A/P. Patients still considered resectable will undergo surgical resection about 4 weeks after completion of neoadjuvant therapy. The goal of surgical resection is completely treating all of their disease by either resection and/or ablation. Patients with bilobar disease must have all of their disease treated in a single operation. Synchronous primary

colorectal and metastatic hepatic tumors are eligible, provided all disease can be resected in a single operation. We will collect peripheral blood and tumor tissue at the time of surgical resection, if applicable, or by re-biopsy if resection is not possible.

Patients deemed unresectable will be managed according to their individual cancer center's disease group management team and will continue to receive Nivolumab (Arm A and Arm B) +/- vaccine (Arm B) as described below. There is no delay required to proceed with study treatment.

In the event that administration of nivolumab +/- the vaccine is impacting the delivery or tolerability of standard of care therapy, patients will be removed from protocol therapy but will continue to be followed on study.

5.1.4 Adjuvant Therapy

Once patients in the post-operative period are deemed ready to begin therapy (about 6-8 weeks after surgery) or for those subjects that are deemed unresectable and continue with treatment:

- Patients in the control arm (Arm A) will receive 8 cycles of mFOLFOX6 in addition to nivolumab given every 2 weeks through completion of chemotherapy: Cycle 5 – Cycle 12. The treatment order for Arm A is Nivolumab followed by mFOLFOX6.
- Patients in the experimental arm (Arm B) will receive 8 cycles of mFOLFOX6 in addition to nivolumab and FPV-CV301 boosters given every 2 weeks through completion of chemotherapy: Cycle 5 - Cycle 12. For Arm B the order of administration is Nivolumab followed by the vaccination at least one hour prior to mFOLFOX6.

If possible, nivolumab (Arm A and Arm B) +/- the CV301 (Arm B) will be administered on the day (+2 days) that systemic chemotherapy resumes. We will re-collect peripheral blood for evaluation of correlates per the study calendar. For Arm B the order of administration is Nivolumab followed by the vaccination at least one hour prior to mFOLFOX6. A window of +2 days between administration of Nivolumab +/- vaccination and mFOLFOX6 will be allowed. This window will accommodate subjects that receive their chemotherapy locally. If there is more than a 2-day delay for any reason, administration of study drugs should be re-aligned so that the chemotherapy falls within +2 days with the next cycle.

In the event that patients in the experimental arm suffer complications that render them unfit for adjuvant systemic chemotherapy or that they cannot complete their adjuvant systemic chemotherapy due to toxicity, patients will still be eligible to receive their scheduled nivolumab and/or CV301 provided the investigators deem them fit enough to do so.

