5.1.5 Maintenance Therapy

Maintenance therapy should start 4 weeks after completion of adjuvant therapy.

- Patients in the control arm (Arm A) will receive nivolumab alone on Day 1 of every 4 week cycle for up to 24 cycles (Cycles 13-36).
- Patients in the experimental arm (Arm B) will receive nivolumab on Day 1 of every 4 week cycle for up to 24 cycles (Cycles 13-36) and FVP-CV301 will be given concomitant every twelve weeks (every 3 cycles) for 8 doses.

Post-therapy patients will be under surveillance per NCCN guidelines with repeat CEA every 3 months for 2 years followed by every 6 months for 1 year (total 3 years), repeat CT of the C/A/P every 3 months for 2 years followed by every 6 months for up to 1 year (total 3 years), and colonoscopy at one year with repetition based on findings at the time of the procedure.

In the event of recurrence, the patient's disease and next line of therapy will be managed according to the individual cancer center's disease group management team. If the recurrence is within two years, the patient will continue to receive their scheduled nivolumab ± vaccine. In the event that administration of nivolumab ± vaccine is impacting the delivery or tolerability of standard of care next line therapy, patients will be removed from protocol therapy but will continue to be followed on study.

5.2 mFOLFOX6

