5.4 Nivolumab Dosing

Nivolumab is safe and well tolerated up to 10mg/kg Q2W. For this study, the standard every 2-week Nivolumab dose of 240 mg IV (identical to a dose of 3 mg/kg for subjects weighing 80 kg) was selected based on clinical data, modeling and simulation approaches using population PK and exposure-response analyses of data from studies in multiple tumor types (melanoma, NSCLC, and renal cell carcinoma) where body weight normalized dosing (mg/kg) has been used. Pre-operatively, participants will receive nivolumab at a dose of 240 mg as a 30 minute infusion every 2 weeks (starting with chemotherapy in the control arm Cycles 1-4 and starting with the vaccine in the experimental arm Days -28, -14 then Cycles 1-4). Post-operatively nivolumab will be given at a dose of 240 mg IV every 2 weeks concurrently with chemotherapy \pm vaccine for 8 chemotherapy cycles (Cycles 1-8). After Cycle 8 (completion of chemotherapy), nivolumab will be given concurrently with the vaccine. Nivolumab will be given every 4 weeks at the standard every 4-week dosing of 480 mg IV for up to 24 cycles and the vaccine will be given every 12 weeks. An infusion window of \pm 10 minutes may be applied.

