6. TOXICITIES AND DOSE DELAYS/DOSE MODIFICATIONS

Guidelines for dose delays and dose modifications are described below, and applicable to the start of each cycle as well as during the cycle if treatment-related toxicities occur. Subjects enrolled in this study will be evaluated clinically and with standard laboratory tests before and at regular intervals during their participation in this study as specified in Study Calendar & Evaluations. The NCI Common Terminology Criteria for Adverse Events (CTCAE) v4 will be used to grade adverse events. Subjects will be evaluated for adverse events (all grades), serious adverse events, and adverse events requiring study drug interruption or discontinuation as specified in Study Calendar & Evaluations.

Dose modifications are always based on the dose used in the previous cycle.

The investigator may attribute each toxicity event to the vaccine, nivolumab, mFOLFOX6, or any component of the combination therapy. Reduction or holding of one agent and not the other agent is appropriate if, in the opinion of the investigator, the toxicity is related to one of the study drugs. For example, if mFOLFOX6 is held due to an AE attributed to that component or the combination, then the vaccine and/or Nivolumab may continue to be administered. The drug to which the investigator is attributing the AE must be documented. If there is more than a 2-day delay for any reason, administration of study drugs should be re-aligned so that the chemotherapy falls within +2 days with the next cycle.

6.1 mFOLFOX6

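### Section 5.1.4 expressly lets only the experimental arm continue nivolumab without adjuvant chemotherapy, leaving a narrow Arm A gap in a background drug

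*Combined protocol and SAP*

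**What the plan says.** Section 5.1.4 describes adjuvant treatment in each arm as eight cycles of mFOLFOX6 with nivolumab every two weeks, plus FPV-CV301 in Arm B. Its last paragraph deals with patients who cannot have, or cannot finish, that chemotherapy. It begins "In the event that patients in the experimental arm suffer complications that render them unfit for adjuvant systemic chemotherapy", adds those whose toxicity stops them completing it, and says that they remain eligible for scheduled nivolumab and/or CV301 if the investigators judge them fit enough. Arm A is not mentioned.

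The paragraph just before names both arms when both are meant: "If possible, nivolumab (Arm A and Arm B) +/- the CV301 (Arm B) will be administered on the day".

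Three other places deal with nivolumab when the planned course is disturbed:

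- Section 5.1.3, unresectable patients: they "will continue to receive Nivolumab (Arm A and Arm B) +/- vaccine (Arm B) as described below".
- Section 5.1.5, recurrence within two years: "the patient will continue to receive their scheduled nivolumab", with or without vaccine. No arm is singled out.
- Section 6, mFOLFOX6 held for an adverse event attributed to it or to the combination: "then the vaccine and/or Nivolumab may continue to be administered". Again no arm is named.

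Section 12.6 makes every patient who had one dose of protocol therapy and was completely resected evaluable for efficacy. Sections 9.7.1 and 12.2.1 count OS from metastasectomy.

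**The concern.** The only intended differences between the arms are CV301 and the two lead-in nivolumab doses that Arm B receives with it. A rule on continuing nivolumab therefore has no evident reason to depend on arm, and the documents give none. Because the protocol labels arms with care elsewhere, a site could reasonably take the one-arm wording as deliberate.

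If it did, two patients in the same clinical situation after liver surgery could be handled differently: nivolumab continued in Arm B, withheld in Arm A. Both would be in the efficacy set, and the divergence would arise after the OS clock has started. No blinding is described, so sites would apply the sentence knowing the arm. Part of any observed difference could then reflect nivolumab and not the vaccine.

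**Working it through.** The point rests on text, and the plan has no figure to reproduce. The check is to set every rule on nivolumab without planned chemotherapy side by side, by arm and by reason.

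| Situation | Arm A | Arm B | Source |
|---|---|---|---|
| Unresectable after neoadjuvant therapy | Continues | Continues | 5.1.3 |
| Recurrence within two years | Continues | Continues | 5.1.5 |
| mFOLFOX6 held for attributed toxicity | May continue | May continue | Section 6 |
| Resected, recurrence-free, unfit for adjuvant chemotherapy for another reason (e.g. surgical complication) | No express statement | Expressly eligible, if judged fit | 5.1.4 |

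**Does section 6 close the last row?** No. Its permission depends on the toxicity being attributed to a study drug. A complication of hepatectomy need not be.

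**Does anything stop nivolumab in Arm A?** No. Section 6.3 lists reasons to delay or permanently stop nivolumab, and section 6.4 lists reasons to stop protocol therapy. Neither names loss of chemotherapy, and neither depends on arm.

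**Does anything favour continuing it?** Yes, indirectly. The section 7 calendar puts mFOLFOX6 and nivolumab on separate rows and marks nivolumab for both arms in Cycles 5-12 and 13-36, using a B only for the two lead-in visits. Section 6.3 lets the investigator delay nivolumab for an adverse event or intercurrent illness and resume it later.

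**Scale.** Section 12.3 plans 35 resected patients per arm, so one affected control is 1/35 = 2.9% of the arm. The documents give no rate of patients unable to start adjuvant chemotherapy, and nothing from which to derive the effect of nivolumab on OS. The calculation stops there.

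**Planned nivolumab doses.** These are needed only to cost the fix. Arm A: 4 (Cycles 1-4) + 8 (Cycles 5-12) + up to 24 (Cycles 13-36) = at most 36. Arm B adds the doses in section 5.1.2 ("The experimental arm (Arm B) will receive two doses of Nivolumab and MVA-CV301 each given Days -28, -14"): 2 + 4 + 8 + 24 = at most 38. The difference of 2 is a declared design feature and not part of this point.

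**The case against.** The strongest reply is that the gap is only silence, and that the plan read as a whole points to continuation in Arm A. The calendar, the delay-and-resume rules and the stopping lists do not depend on arm, and controls keep nivolumab in all three neighbouring situations. Same-day dosing with chemotherapy is asked for only where possible. On that reading, withholding nivolumab from this one kind of control would be the anomaly. The harm also needs a chain of conditions: a control who is resected, recurrence-free, lastingly unfit for mFOLFOX6 for a reason not attributed to study drug, yet fit for nivolumab, at a site that treats silence as a bar. The Arm B sentence is itself conditional on fitness, and post-operative therapy may simply wait until the patient is ready (section 7, footnote 7).

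Most of this stands, and it limits the point to a small one. It does not make the sentence adequate. The plan is explicit for one arm and silent for the other in the same situation, so equal handling depends on each site's inference.

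A reader might infer that controls are forbidden nivolumab without chemotherapy. The documents do not say so; three provisions allow it and none prohibits it.

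A reader might also count the missing chemotherapy-free schedule as part of the imbalance. Section 5.4 says "Post-operatively nivolumab will be given at a dose of 240 mg IV every 2 weeks concurrently with chemotherapy", and section 5.1.5 says "Maintenance therapy should start 4 weeks after completion of adjuvant therapy"; neither says what to do if chemotherapy is never started. That omission is real but applies equally to both arms, so it is not evidence of an arm difference.

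**Conclusion.** The point holds in a narrow form. For a resected, recurrence-free patient unfit for adjuvant chemotherapy for a reason other than attributed toxicity, continued nivolumab is expressly allowed in Arm B and not addressed in Arm A. This could produce an arm difference in a background drug among efficacy-evaluable patients. It is a possibility, not a demonstrated bias, and it depends on some sites reading section 5.1.4 literally.

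The impact is probably small. It is tempting to put a number on lost control-arm doses or on the OS comparison. The documents support neither: any dose total would need an invented count of affected patients and a choice among readings of the maintenance rule, and the direction and size of an OS effect cannot be derived. The sample size, the one-sided 2.5% log-rank test and the efficacy set are unaffected. The wording should still be corrected, because the asymmetry is avoidable and cheap to remove.

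**What to change.** In the last paragraph of section 5.1.4:

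- make the provision apply to patients in either arm instead of the experimental arm alone;
- state what may continue as scheduled nivolumab (Arm A and Arm B) and/or CV301 (Arm B);
- keep the condition that the investigators judge the patient fit enough.

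Which nivolumab schedule to use when chemotherapy is not given is for the sponsor to decide, since the documents do not show which was intended. Whatever is chosen should be the same in both arms.

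The cost is a minor protocol amendment, with the IRB step in section 15.1, and possibly slightly more nivolumab in the control arm. No control patient would exceed the planned maximum of 36 doses. Sample size, alpha and power do not change.

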5.1.5 Maintenance Therapy

Maintenance therapy should start 4 weeks after completion of adjuvant therapy.

- Patients in the control arm (Arm A) will receive nivolumab alone on Day 1 of every 4 week cycle for up to 24 cycles (Cycles 13-36).
- Patients in the experimental arm (Arm B) will receive nivolumab on Day 1 of every 4 week cycle for up to 24 cycles (Cycles 13-36) and FVP-CV301 will be given concomitant every twelve weeks (every 3 cycles) for 8 doses.

Post-therapy patients will be under surveillance per NCCN guidelines with repeat CEA every 3 months for 2 years followed by every 6 months for 1 year (total 3 years), repeat CT of the C/A/P every 3 months for 2 years followed by every 6 months for up to 1 year (total 3 years), and colonoscopy at one year with repetition based on findings at the time of the procedure.

In the event of recurrence, the patient's disease and next line of therapy will be managed according to the individual cancer center's disease group management team. If the recurrence is within two years, the patient will continue to receive their scheduled nivolumab ± vaccine. In the event that administration of nivolumab ± vaccine is impacting the delivery or tolerability of standard of care next line therapy, patients will be removed from protocol therapy but will continue to be followed on study.

5.2 mFOLFOX6

5.2.1 Preparation and Administration

For detailed information on these agents, refer to the FDA approved package inserts. Institutional standards may be utilized for the preparation and administration of mFOLFOX6 including windows for infusion times. mFOLFOX6 will be administered as a combination regimen (see Table below) every 14 days for 4 cycles prior to surgery then every 14 days for 8 cycles after surgery after clearance to resume chemotherapy at the discretion of the performing surgeon. Subjects that do not proceed to surgery may begin chemotherapy

A histamine-2 (H2) antagonist, a histamine-1 (H1) antagonist, and a steroid may be used as premedications to decrease the risk of hypersensitivity reactions.

Consider the below premedication supportive care regimen; institutional standards may be used for premedication supportive care regimen.

Ondansetron 24 mg PO prior to Chemotherapy

Dexamethasone 12 mg PO

Ondansetron 8 mg PO every 12 hours for 2 days

Dexamethasone 8 mg PO every 12 hours for 2 days

Prochlorperazine 10mg IV/PO q6hr PRN Nausea/Vomiting

5.2.2 mFOLFOX6 Dosing

The recommended doses and routes of administration for the mFOLFOX6 should be made according to institutional guidelines, but a typical dose/schedule is detailed in the table below. Windows for administration may be utilized as per institutional standards including windows for infusion times.

*For oxaliplatin doses \leq 104 mg use 250 mL D5W.

Drug	Dose Per Unit	Route	Total Volume and Rate
Oxaliplatin*	85 mg/m ²	IVPB	D5W 250-500 mL over 2 hours
Leucovorin	400 mg/ m ²	IVPB	NS 250 mL over 2 hours
Fluorouracil	400 mg/ m ²	IVP	Over 5 minutes after leucovorin
Fluorouracil	2400 mg/ m ²	IVCI	Diluted in NS over 46 hours

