5.2.2.1 Oxaliplatin

- Oxaliplatin administration must always precede the administration of 5-FU.
- Oxaliplatin may be given at the same time as leucovorin in separate bags using a Y connector (providing trometamol is not used as an excipient).
- Oxaliplatin may not be administered with fluorouracil.
- Do not use with injection equipment containing aluminum, as this can degrade platinum compounds.
- Oxaliplatin causes irritation if extravasated (follow local policy).
- Acute neurotoxicity is common with oxaliplatin and can be precipitated on exposure to cold, therefore cryotherapy should be avoided.
- Infuse IV over 2 hours. Increasing infusion time to 6 hours may decrease acute toxicity such as pharyngolaryngeal dysesthesia.
- Unopened vials should be stored at 15-30°C; protect from light.

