5.2.2.2 Leucovorin

- Leucovorin may be given at the same time as oxaliplatin in separate bags using a Y connector (providing trometamol is not used as an excipient).
- Leucovorin must be given prior to fluorouracil (enhances the effects of fluorouracil by increasing fluorouracil binding to target enzyme thymidylate synthetase).
- Infuse IV over 2 hours using CADD pump or similar device.

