6.1.8 Pharyngolaryngeal Dysesthesia

Acute pharyngolaryngeal dysesthesia occurs in 1-2% of patients. It is characterized by subjective sensations of dysphagia and dyspnea without objective evidence of respiratory distress, laryngospasm or bronchospasm (e.g. cyanosis, hypoxia, wheezing, stridor). Symptoms are often precipitated by exposure to cold. The symptoms are rapidly reversible in the absence of treatment, but antihistamines and bronchodilators may be administered. Increasing the infusion time from 2 to 6 hours helps reduce the incidence of this syndrome.

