10.2.1 Oxaliplatin

Oxaliplatin is a platinum alkylating agent, which contains platinum complexed to oxalate and diaminocyclohexane (DACH) complex. Platinum complexes are formed intracellularly and inhibit DNA synthesis through covalent binding of DNA molecules to form intrastrand and interstrand DNA cross-links. Oxaliplatin differs molecularly, from other platinums (cisplatin and carboplatin), by its bulky DACH carrier ligand that most likely accounts for both its efficacy and lack of cross-resistance with other platinum compounds. Cytotoxicity is cell-cycle nonspecific. Oxaliplatin is a radiosensitizing agent.

*Oxaliplatin is incompatible with 0.9% NaCl.

*Oxaliplatin is incompatible in solution with alkaline medications or media and must not be mixed with these.

*Storage and handling materials containing aluminum parts that may come in contact with oxaliplatin should not be used for preparation or mixing of the drug, as aluminum can degrade platinum compounds.

- 1) The lyophilized powder is reconstituted by adding 10 mL (for the 50 mg vial) or 20 mL (for the 100 mg vial) of Water for Injection, USP or 5% Dextrose Injection, USP. Do not administer the reconstituted solution without further dilution.
- 2) After reconstitution in the original vial, the solution may be stored up to 24 hours under refrigeration [2° to 8°C (36° to 46° F)]. Do not freeze the concentrated solution.
- 3) The solution must be further diluted in an infusion solution of 250-500 mL of D5W. A final dilution must never be performed with a sodium chloride solution or other chloride-containing solutions. Concentration must be between 0.2 to 0.7 mg/mL.
- 4) After final dilution with D5W, the shelf life is 6 hours at room temperature [20° to 25°C (68° to 77°F)] or up to 24 hours under refrigeration [2° to 8°C (36° to 46°F)].
- 5) Store under normal lighting conditions at 20°-25°C (68°-77°F); excursions permitted to 15-30°C (59- 86°F). Do not freeze.

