10.2.2 Leucovorin

Leucovorin calcium (folic acid) is a reduced form of folic acid. It is usually used 24 hours after methotrexate to selectively “rescue” normal cells from the adverse effects of methotrexate caused by inhibition of production of reduced folates. It is not used simultaneously with

methotrexate, as it might then nullify the therapeutic effect of the methotrexate. Leucovorin has also been used to enhance the activity of fluorouracil by binding to the enzyme thymidylate synthetase and decreasing intracellular levels of thymidylate. Leucovorin is available in D and L stereoisomers; the L stereoisomer is the active moiety.

* Each 50, 100, and 200 mg vial of Leucovorin when reconstituted with 5, 10, and 20 mL, respectively, of sterile diluent yields a leucovorin concentration of 10 mg per mL. Each 350 mg vial of Leucovorin when reconstituted with 17.5 mL of sterile diluent yields a leucovorin concentration of 20 mg per mL. *Leucovorin should not be mixed in the same infusion as fluorouracil as a precipitate may form.

- 1) Reconstitute the lyophilized vial products with Bacteriostatic Water for Injection, USP (benzyl alcohol preserved), or Sterile Water for Injection, USP. When reconstituted with Bacteriostatic Water for Injection, the resulting solution must be used within 7 days. If the product is reconstituted with Sterile Water for Injection, use immediately and discard any unused portion. Because of the benzyl alcohol contained in Bacteriostatic Water for Injection, when doses greater than 10 mg/m² are administered, Leucovorin should be reconstituted with Sterile Water for Injection, and used immediately.
- 2) Dilute leucovorin in 50-1000 mL D5W or NS for infusion. Leucovorin may be mixed in 50mL NS or D5W minibag (doses up to 500mg) or 100mL minibag (doses >500mg) or in 100mL fluid in graduated administration set (D5W, NS or 2/3-1/3). Parenteral admixture is stable for 24 hours stored at room temperature (25°C) and for 4 days when stored under refrigeration (4°C).
- 3) Lyophilized powder vials should be stored at 20° to 25°C (68° to 77° F). Solution for injection should be stored in refrigerator 2° to 8°C (36° to 46°F). Protect from light. Retain in carton until time of use.

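### The mFOLFOX6 administration text permits, without requiring, leucovorin in saline to share a Y line with oxaliplatin, which conflicts with the saline incompatibility stated in 10.2.1

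*Combined protocol and SAP*

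**What the plan says.** All the text is in the combined protocol and SAP.

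- **Section 5.2.2, dosing table.** The leucovorin row reads "NS 250 mL over 2 hours" and the oxaliplatin row "D5W 250-500 mL over 2 hours". The table is introduced as a typical schedule, subject to institutional guidelines. Section 5.2.1 also lets sites use their own standards for preparation and administration, and refers them to the package inserts.
- **Section 5.2.2.1.** "Oxaliplatin may be given at the same time as leucovorin in separate bags using a Y connector". The one proviso is that trometamol is not an excipient.
- **Section 5.2.2.2.** "Leucovorin may be given at the same time as oxaliplatin in separate bags using a Y connector", with the same single proviso.
- **Section 10.2.2.** "Dilute leucovorin in 50-1000 mL D5W or NS for infusion". No exception is made for concurrent infusion.
- **Section 10.2.1.** "Oxaliplatin is incompatible with 0.9% NaCl". A separate preparation step in the same section forbids making the final oxaliplatin dilution with sodium chloride or any other chloride-containing solution.

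**The concern.** A pharmacist or nurse working from section 5 sees two infusions of equal length, an explicit permission to run them together, and one compatibility condition. Because that condition names trometamol, a reader could take it as the complete list. The saline incompatibility is stated only in the drug-information section, away from the table and from both Y-connector permissions. The aluminum warning, by contrast, appears in both 5.2.2.1 and 10.2.1.

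What is at stake is drug handling and patient safety: the protocol's administration text allows a combination that its own drug-information text describes as incompatible. The chemotherapy is common to both arms and is planned for every neoadjuvant and adjuvant cycle. It is not a question of inference for the survival comparison.

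**Working it through.** The documents give no figure to reproduce, so the check sets the passages side by side and asks whether any of them blocks the combination.

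1. **Diluent.** The 5.2.2 table gives NS for leucovorin, and 10.2.2 allows NS or D5W. A leucovorin bag in NS therefore satisfies both. NS is not in the list of abbreviations; it is read here in its usual sense of 0.9% sodium chloride.
2. **Timing.** The table gives both drugs 2 hours, so running them concurrently fits the printed schedule.
3. **Route.** Sections 5.2.2.1 and 5.2.2.2 allow concurrent infusion from separate bags through a Y connector if trometamol is absent. Neither sets a condition on the leucovorin diluent.
4. **Result of 1 to 3.** Leucovorin in NS and oxaliplatin in D5W, joined at a Y connector, meet every condition in 5.2.2, 5.2.2.1, 5.2.2.2 and 10.2.2. Below the Y, oxaliplatin and saline share a line.
5. **Against 10.2.1.** The general incompatibility statement names 0.9% NaCl and is not limited to preparing the bag. The combination in step 4 conflicts with it. The stricter prohibition in 10.2.1 concerns the final dilution, and step 4 does not breach that one, because the oxaliplatin bag itself is in D5W.
6. **Is the route closed elsewhere?** For fluorouracil, whose continuous infusion is also listed in NS, 5.2.2.1 rules out giving it with oxaliplatin. No equivalent restriction covers leucovorin in NS.

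**Ceiling on exposure.** Each patient is planned to receive 4 + 8 = 12 cycles. At the enrolment cap, 12 × 78 = 936 administrations; at the planned enrolment of 74, 12 × 74 = 888. These are counts of planned mFOLFOX6 administrations if every patient completes every cycle. They do not estimate how many would use the combination in step 4. The floor is zero.

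**The case against.** The strongest reply is that nothing here tells a site to mix the two. Co-infusion is optional, D5W is an allowed leucovorin diluent, the table is only typical, and institutional standards and package inserts may override it. Section 10.2.1 belongs to the same protocol, so a site that reads the whole document has routes that satisfy every passage. The explicit prohibitions in 10.2.1 concern the final dilution and the mixing of oxaliplatin with alkaline products; applying its general saline line to contact below a Y connector is an inference.

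Most of this stands, and it limits how strongly the point can be put: contact is permitted, not instructed, and its frequency is unknown. It does not remove the conflict. The incompatibility sentence stands on its own without a stated scope, and the protocol's own worked example supplies the diluent that conflicts with it.

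Two stronger readings are tempting and are not supported.

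- **Delivered dose.** A reader might infer that the oxaliplatin delivered would differ from the dose recorded. Section 10.2.1 states an incompatibility but not its consequence, and the documents contain no stability, loss or line-contact data.
- **Shelf life.** A reader might also set "Increasing the infusion time from 2 to 6 hours helps reduce the incidence of this syndrome" in section 6.1.8 against "the shelf life is 6 hours at room temperature" in 10.2.1 and conclude that no time is left for preparation. The same sentence in 10.2.1 goes on to allow up to 24 hours under refrigeration. It does not say whether infusion time counts towards shelf life or how the two storage periods combine, and the longer infusion is optional. No contradiction follows from the text.

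**Conclusion.** The point holds as an internal inconsistency with a bearing on safety. The table row, the two Y-connector permissions and the leucovorin diluent options together permit oxaliplatin to meet saline in a shared line, against the general incompatibility statement in 10.2.1.

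The number of administrations affected cannot be determined. It lies between none and all of those given, depending on how many sites combine the printed diluent with a Y connector. The totals of 936 and 888 should not be read as numbers exposed.

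The conclusion rests on two readings: that NS means 0.9% sodium chloride, and that the unqualified incompatibility line extends to contact in the line as well as in the bag. The sponsor can confirm or correct both. Because both arms receive the same chemotherapy under the same text, the wording itself creates no systematic difference between them. The one-sided 2.5% test, the 80% power and the 70 resected patients are unaffected.

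**What to change.** The sponsor, with pharmacy input, should reconcile the leucovorin row of the 5.2.2 table, the Y-connector permissions in 5.2.2.1 and 5.2.2.2, and the diluent options in 10.2.2 with the incompatibility statement in 10.2.1, so that all five places agree. The edit should make clear whether the 10.2.1 statement covers contact in a shared line or only preparation of the bag, and the administration sections should carry or cross-refer to whatever compatibility conditions result. Which entry changes is for the sponsor and pharmacy to decide; this review takes no position on it.

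The cost is a protocol clarification and a pharmacy check. It adds no patients, visits or procedures. Depending on the outcome, some sites may need to revise a standing order.
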